## **9.6. Primary Analysis**

Primary analysis for this study will occur after all subjects have either completed the study or completed 12 months of treatment. Subjects who are still active at the time of the primary analysis may continue on study until disease progression or medication intolerance is observed.

## **10. MONITORING, RECORDING, AND REPORTING OF ADVERSE EVENTS**

### **10.1. Toxicities of Nab-Sirolimus**

Nab-Sirolimus is a formulation of rapamycin. No unexpected toxicities not already known for rapamycin (Rapamune®) or the rapamycin prodrug, temsirolimus (Torisel®), were identified in the nonclinical toxicity studies, or observed in the phase 1 studies for nab-Sirolimus.

More details on the known precautions, warnings, and AEs of rapamycin and rapalogs are found in the Rapamune® and Torisel® Package Inserts.

### **10.2. Toxicities of Pazopanib**

Per the Prescribing information, the most common AEs in subjects with advanced STS (greater than or equal to 20%) are fatigue, diarrhea, nausea, decreased weight, hypertension, decreased appetite, hair color changes, vomiting, tumor pain, dysgeusia, headache, musculoskeletal pain, myalgia, gastrointestinal pain, and dyspnea.

### **10.3. Evaluation of Adverse Events**

The investigator must assign the following AE attributes:

- AE diagnosis or syndrome(s), if known (if not known, signs or symptoms)
- Dates of onset and resolution (if resolved)
- Severity [and/or toxicity per protocol]
- Assessment of relatedness to the IP
- Assessment of relatedness to protocol-required procedures
- Action taken

The AE toxicity grading scale used will be the NCI CTCAE Version 5.0.

### **10.4. Serious Adverse Events**

#### **10.4.1. Definition of Serious Adverse Events**

An SAE is defined as an AE that meets at least 1 of the following serious criteria:

- fatal
- life-threatening (places the subject at immediate risk of death)
- requires in-patient hospitalization or prolongation of existing hospitalization
- results in persistent or significant disability/incapacity
- congenital anomaly/birth defect
- other medically important serious event

An AE would meet the criterion of “requires hospitalization”, if the event necessitated an in-patient admission to a health care facility (e.g., overnight stay).

If an investigator considers an event to be clinically important, but it does not meet any of the serious criteria, the event could be classified as an SAE under the criterion of “other medically important serious event”. Examples of such events could include allergic bronchospasm, convulsions, blood dyscrasias, drug-induced liver injury, or events that necessitate an emergency room visit, outpatient surgery, or urgent intervention.

Since the criteria for the CTCAE grading scale differs from the regulatory criteria for SAEs, if AEs correspond to grade 4 “life threatening” CTCAE grading scale criteria (e.g., laboratory abnormality reported as grade 4 without manifestation of life-threatening status), it will be left to the investigator’s judgment to also report these abnormalities as SAEs. For any AE that applies to this situation, comprehensive documentation of the event’s severity status must be recorded in the subject’s medical record.

#### **10.4.2. Reporting Procedures for Serious Adverse Events**

All SAEs that are drug-related and unexpected must be reported by the Sponsor-Investigator to their IRB in writing, and to the FDA within 15 days as required by law.

Any AE that meets any criterion for an SAE requires the completion of an SAE Report Form in addition to being recorded on the AE page/screen of the CRF. All SAEs must be reported to Aadi Bioscience Drug Safety within 24 hours of the Sponsor-Investigator’s knowledge of the event by facsimile, or other appropriate method, using the SAE Report Form, or approved equivalent form. This instruction pertains to initial SAE reports as well as any follow-up reports.

The Sponsor-Investigator or treating investigator is required to ensure that the data on these forms is accurate and consistent. This requirement applies to all SAEs (regardless of relationship to IP) that occur during the study (from the time of signing of the informed consent form to 30 days after the last dose of IP), and those made known to the investigator at any time thereafter that are suspected of being related to IP.

The SAE report should provide a detailed description of the SAE and include a concise summary of hospital records and other relevant documents. If a subject died and an autopsy has been performed, copies of the autopsy report and death certificate are to be sent to Aadi Bioscience Drug Safety as soon as these become available. Any follow-up data will be detailed in a subsequent SAE Report Form, or approved equivalent form, and sent to Aadi Bioscience Drug Safety.

Where required by local legislation, the Sponsor-Investigator is responsible for informing the IRB/EC of the SAE and providing them with all relevant initial and follow-up information about the event. The Sponsor-Investigator must keep copies of all SAE information on file including correspondence with Aadi Bioscience and the IRB/EC.

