Adverse Event Assessment		Continuous from time of consent to 30 days after last study drug					
Survival Assessment							x

a All visits are allowed to occur in a window of  $\pm 3$  days unless otherwise specified.

b Baseline screening visit will be done within 28 days prior to study treatment Day 1. Baseline scans should be completed within 28 days of C1D1, as close to C1D1 as possible.

c Day 15 visit is only in Cycle 1 and 2. Cycle 3+ does not have a Day 15 visit.

d End of Treatment-phase (EOT) Visit should be within  $\pm 3$  days of last study treatment.

e Thyroid function test to be repeated as needed, based on investigator's opinion.

f Subjects who consent for pre-treatment tissue collection for biomarker analysis: either fresh-frozen or formalin-fixed paraffin-embedded (FFPE) tumor blocks or unstained slides (min 10). Fresh tissue collection may only be obtained if clinically feasible and without undue risk to the subject.

g For all female subjects of childbearing potential (see Inclusion 5), a serum pregnancy test will be done at screening. A serum or urine pregnancy test will be repeated within 72 hours before first treatment if the serum pregnancy test occurred  $>72$  hours before dosing, and at EOT and 30-Day Follow-Up (if applicable). Pregnancy tests conducted after screening will be recorded in the source documentation only.

h Single tracing ECG and lipids evaluations are every even cycle (C2, C4, C6, etc.). Only lipid panel at baseline is required to be fasting lipid.

i Height is measured only at C1D1. BSA is calculated ONLY on C1D1; to be recalculated only if the weight changes by  $> 10\%$  in subsequent cycles, at which point the recalculated weight will become the new baseline. Vitals signs to include respiration rate, temperature, systolic/diastolic blood pressure, and pulse. Vital signs to be collected Pre-Dose (within 15 minutes prior to start of infusion) and Post-Dose (+10 minutes from end of infusion).

j Rapamycin levels are done locally and for all subjects in Phase 1 at Cycle 1 Day 1 Post-Dose (within +10 minutes from end of infusion), Cycle 1 Day 1 – 24-hour Post-Dose (optional, +/- 2 hours), Cycle 1 Day 8 and Day 15 anytime, as well as in Cycle 2 Day 1 Pre-Dose (within 15 minutes prior to infusion) and on Cycle 2 Day 8 and Day 15 (anytime).

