## **5.2. Treatment Period**

A subject is considered enrolled on study day 1 when the IP, nab-Sirolimus, is first administered. Nab-Sirolimus is to be administered after all other protocol-specified pre-dose assessments have been performed during each visit that it is required. Subjects will continue therapy until disease progression, unacceptable AEs, or withdrawal of consent.

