### **6.4. Dose Limiting Toxicity**

Dose-limiting toxicities will be assessed in the first 2 cycles (2, 3-week cycles).

A DLT is defined as any Grade 3 or greater AE, at least possibly related to either or both nab-Sirolimus and pazopanib. Only toxicities with a clearly identified and documented alternative explanation may be deemed non-DLT. Dose-limiting toxicities include any death not clearly due to underlying disease or extraneous causes, or persistent intolerable nonhematologic AE of any grade that requires dose reduction or permanent discontinuation of the study-drug, in the opinion of the investigator.

The following adverse events may be excluded from being considered a DLT:

- Grade 3 nausea/vomiting or diarrhea for less than 72 hours, with adequate antiemetic and other supportive care;
- Grade 3 fatigue for less than 1 week;
- Grade 3 or higher electrolyte abnormality that lasts up to 72 hours, is not clinically complicated, and resolves spontaneously or responds to conventional medical interventions.
- Lab abnormalities that have no clinical sequelae (e.g. febrile neutropenia from low ANC, bleeding from thrombocytopenia, etc.) and resolve to grade 1 or better within 7 days will not be considered a DLT.

Nab-Sirolimus dose modification guidelines are outlined in Table 9 and Table 11 for clinically significant toxicities that are deemed related to nab-Sirolimus.

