## 6.5. Dose Modification Algorithms for Adverse Events Possibly Related to nab-Sirolimus and Pazopanib

**Table 11 - Dose Modification Algorithms for Overlapping Adverse Events Possibly Related to nab-Sirolimus and Pazopanib (See also Table 9 and Table 10)**

System/Organ	Adverse Event	CTCAE Grade v5.0	Dose Modification Algorithm
Hematologic toxicity	Thrombocytopenia, Anemia	Grade 2	
Nab-Sirolimus: Nab-Sirolimus can be administered if meeting the following hematological requirements: platelets <math>>100 \times 10^9/L</math> and hemoglobin <math>\geq 8</math> g/dL.
 
Pazopanib: No changes to pazopanib dosing.

		Grade 3-4	
nab-Sirolimus: Hold nab-Sirolimus immediately for the remainder of that cycle. Repeat blood collection within 3 days. Nab-Sirolimus can resume once meeting following requirements: platelet count <math>>100 \times 10^9/L</math> and hemoglobin <math>\geq 8</math> g/dL. For 2nd and subsequent events, drug will be restarted at a reduced dose; G-CSF may be given as deemed indicated.
 
Pazopanib: Delay pazopanib until platelets <math>\leq</math> grade 1, resume pazopanib with one dose level reduction.

	Neutropenia, Febrile or Afebrile	Grade 3	
nab-Sirolimus: Hold nab-Sirolimus. Repeat blood collection within 3 days. Nab-Sirolimus can resume once meeting following requirements: absolute ANC <math>\geq 1.5 \times 10^9/L</math>. For 2nd and subsequent events, drug will be restarted at a reduced dose; G-CSF may be given as deemed indicated.
 
Pazopanib: Delay pazopanib until <math>\leq</math> grade 2, and then resume pazopanib at the current dose level.

		Grade 4	
Nab-Sirolimus: Hold nab-Sirolimus. Repeat blood collection within 3 days. Nab-Sirolimus can resume once meeting following requirements: absolute ANC <math>\geq 1.5 \times 10^9/L</math>. For 2nd and subsequent events, drug will be restarted at a reduced dose; G-CSF may be given as deemed indicated.
 
Pazopanib: Delay pazopanib until <math>\leq</math> grade 2, then resume pazopanib with one dose level reduction.

Hepatic Toxicity	Hepatic Failure	Grade 3	
Nab-Sirolimus: See Section 6.1.3.1 and 6.1.3.2.
 
Subjects with ALT/AST > 3 x ULN, or Total Bilirubin > 3 x ULN, or Alk Phos > 8 x ULN are recommended for withholding of nab-Sirolimus.
 
Pazopanib: Discontinue pazopanib.

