### 9.2. Safety Analysis

The safety analysis set includes all treated subjects.

Safety and tolerability will be monitored through continuous reporting of treatment emergent and TRAEs, AEs of special interest, laboratory abnormalities, and incidence of subjects experiencing dose modifications, dose delay/dose not given, dose interruptions, and/or premature discontinuation of IP due to an AE. All AEs will be recorded by the investigator from the time the subject signs informed consent until 30 days after the last dose of protocol therapy. Adverse events will be graded by NCI CTCAE v5.0.

Physical examination, vital signs, laboratory assessments (e.g., serum chemistry, hematology), and ECOG performance status will be monitored and reviewed per institutional standards. All SAEs (regardless of relationship to IP) will be followed until resolution. Local laboratory analysis will be performed as per study schedule.

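### The SAE reporting window is tied to nab-Sirolimus alone, while AE recording follows both drugs, and relatedness to pazopanib is not among the required AE attributes

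*Combined protocol and SAP*

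**What the plan says.** **SAE window.** Section 10.4.2 applies the SAE requirement, whatever the relationship to the IP, "from the time of signing of the informed consent form to 30 days after the last dose of IP". After that it covers only "those made known to the investigator at any time thereafter that are suspected of being related to IP".

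**Meaning of IP.** The synopsis lists nab-Sirolimus as the investigational product and gives pazopanib its own row as the FDA-approved agent. Section 5.2 dates enrollment from the day "when the IP, nab-Sirolimus, is first administered". Section 11.3 names the IP and other protocol-required therapies separately.

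**AE window and visits.** Tables 4 and 5 set AE assessment as "Continuous from time of consent to 30 days after last study drug", and Section 9.2 records AEs "until 30 days after the last dose of protocol therapy". The abbreviations table and Section 2.4 define End of Treatment, and time the 30-Day Follow-Up Visit, from the later of the two drugs.

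**Causality.** Section 10.3 lists "Assessment of relatedness to the IP" and relatedness to protocol-required procedures. It has no item for pazopanib. Section 6.4 defines a DLT by events "at least possibly related to either or both nab-Sirolimus and pazopanib", and Tables 10 and 11 apply to events possibly related to pazopanib or to both drugs.

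**The concern.** Pazopanib is taken daily, whereas nab-Sirolimus on the current schedule is given once every 21 days and can be held. The last pazopanib dose can therefore fall well after the last nab-Sirolimus dose, and an SAE clock that starts from nab-Sirolimus alone then runs out early. Tables 10 and 11 name haemorrhage, perforation, thromboembolic events and hepatic failure among the events that require action on pazopanib. A site that follows Section 10.4.2 as written could leave such an event off the SAE Report Form and the 24-hour report when it occurs during or soon after pazopanib exposure.

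The causality list raises a second, separate issue. The phase 1 primary endpoint turns on relatedness to either drug, but the attributes the investigator must assign do not include one of them. In the 3+3 rule of Section 2.3, 0 of 3 subjects with a DLT escalates, 1 of 3 expands the cohort, and 2 or more ends enrollment at that level. A single inconsistently attributed event can therefore change a dose decision.

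**Working it through.** The plan states no figure for this point, so there is none to reproduce. The check is day counting.

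**Inputs**
- SAE window: 30 days after the last nab-Sirolimus dose (Section 10.4.2, with IP read as in the synopsis and Section 5.2).
- AE window: 30 days after the last dose of either drug (Section 9.2, Tables 4 and 5).
- Dosing interval: 21 days on the Day 1-only schedule (Sections 1.5 and 2.3).
- Permitted hold for toxicity: up to 21 days, longer with Sponsor-Investigator approval (Section 6.1.2).
- Pazopanib can continue while nab-Sirolimus waits. In Table 11, the grade 2 thrombocytopenia/anemia row makes nab-Sirolimus depend on blood counts and says "No changes to pazopanib dosing". The stomatitis row of Table 9 holds only nab-Sirolimus.

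**Formulas.** Let G be the days from the last nab-Sirolimus dose to the last pazopanib dose.
- SAE cover after the last pazopanib dose = 30 − G (negative means the window closed first).
- AE cover after the last pazopanib dose = 30.
- Shortfall of the SAE window against the AE window = (G + 30) − 30 = G.

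| Situation | G | SAE cover after last pazopanib dose | Shortfall against AE window |
|---|---|---|---|
| Both drugs stop when the next Day 1 dose is due | 21 | 30 − 21 = 9 days | 21 days |
| 21-day hold, pazopanib continued, no restart | 21 + 21 = 42 | 30 − 42 = −12 days | 42 days |
| Day 1/Day 8 schedule, last dose on Day 8, same hold | 14 + 21 = 35 | 30 − 35 = −5 days | 35 days |

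**In study days**, with the last nab-Sirolimus dose on Cycle 2 Day 1 (day 22), the SAE window closes on day 22 + 30 = 52.
- Both drugs stop on day 43: AE recording ends on day 43 + 30 = 73, and 73 − 52 = 21 days. The SAE window is still open when pazopanib stops (52 − 43 = 9 days).
- The dose due on day 43 is held for 21 days and both drugs then stop, on day 64: AE recording ends on day 64 + 30 = 94. The SAE window closed 64 − 52 = 12 days before the last pazopanib dose and 94 − 52 = 42 days before AE recording ends.

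Holds beyond 21 days widen both gaps. With the window anchored to the later drug, it would close with AE recording: day 72 after the last nab-Sirolimus dose in the 42-day case (42 + 30), instead of day 30.

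**Causality.** Set side by side, Section 10.3 yields two attributes (IP, procedures) and Section 6.4 needs two (nab-Sirolimus, pazopanib). Only nab-Sirolimus is common to both. Table 3 shows that the missing one can matter: it counts one proteinuria DLT, an event listed in Table 10 for pazopanib but not in Table 9 for nab-Sirolimus.

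**The case against.** Several points on the other side have force.

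- **The events are not lost.** AEs are recorded to 30 days after either drug, and Section 9.2 follows all SAEs to resolution whatever their relationship to the IP. DLTs and the safety analysis come from AEs, not from SAE forms. A reader might infer that the short window biases the DLT count or the safety profile downward; the documents do not support that.
- **Other reporting duties are wider.** The sentence in Section 10.4.2 on drug-related, unexpected SAEs going to the IRB and FDA does not name a drug or an end date. The next paragraph requires an SAE form for any qualifying AE, again without a window. The 30-day sentence comes after one about the accuracy of the forms, so its reach is arguable. This stands: it would be wrong to say these events leave expedited reporting altogether. The ambiguity is itself a reason to fix the wording.
- **Section 2.4 narrows the route.** A subject who must discontinue nab-Sirolimus is discontinued from the study, and single-agent continuation is stated only for nab-Sirolimus. Table 11 also delays pazopanib in grade 3–4 thrombocytopenia/anemia and grade 3 or 4 neutropenia. The window therefore closes during pazopanib use mainly when a hold with pazopanib continued is never resumed. A hold is not a discontinuation, however, and Section 2.4 itself defines End of Treatment by the later drug. The 9-against-30-day difference remains even when both drugs stop together.
- **Section 6.4 has its own attribution test.** Only a toxicity with a clear, documented alternative explanation may be deemed non-DLT, so attribution to pazopanib does not exempt an event. The proteinuria in Table 3 was counted. The CRF is not among the documents and may hold a pazopanib field. A reader might infer that pazopanib-related DLTs cannot be recognised; that goes too far.

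**Conclusion.** The mismatch stands. On Day 1-only dosing the SAE window covers 9 rather than 30 days after the last pazopanib dose when both drugs stop at the next due infusion. This ordinary case does not show the window closing during pazopanib use. That happens in the held case, where it closes 12 days before the last pazopanib dose and 42 days before AE recording ends.

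What lapses is chiefly the SAE Report Form and the 24-hour report to the manufacturer, for events attributed to pazopanib alone or to neither drug. Late SAEs suspected to be related to nab-Sirolimus stay reportable. The omission in Section 10.3 creates a risk, not a certainty, of inconsistent DLT attribution.

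The conclusion assumes that IP means nab-Sirolimus alone, that the 30-day sentence governs the reporting duty, and, for the held case, that pazopanib is taken throughout a full 21-day hold with no restart. The documents give no frequency for that sequence. Section 1.5 reports missed or delayed doses in 12 of the first 13 subjects, but on the Day 1/Day 8 schedule and without saying whether pazopanib continued.

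**What to change.** - **Section 10.4.2:** end the SAE window 30 days after the last dose of nab-Sirolimus or pazopanib, whichever is later, and extend the late-SAE clause to events suspected to be related to either drug. State plainly that this window governs the SAE Report Form and the 24-hour report.
- **Section 10.3:** record relatedness to nab-Sirolimus and to pazopanib as separate attributes, and use both to classify DLTs under Section 6.4.

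The cost is protocol wording, one causality field on the CRF and a few more SAE reports. No visit, subject or dosing rule changes.

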#### **10.5. Pregnancy and Breastfeeding Reporting**

If a pregnancy occurs in a female subject, or female partner of a male subject, while the subject is taking protocol-required therapies, report the pregnancy to Aadi Bioscience as specified below. In addition to reporting any pregnancies occurring during the study, investigators should monitor for pregnancies that occur up to 3 months after the last dose of protocol-required therapies.

The investigator will follow the female subject until completion of the pregnancy, and must notify Aadi Bioscience Drug Safety immediately about the outcome of the pregnancy (either normal or abnormal outcome) using the Pregnancy Follow-up Report Form, or approved equivalent form, if the female subject consents to allow the study team to follow the pregnancy to completion or termination.

If a lactation case occurs while the female subject is taking protocol-required therapies, report the lactation case to Aadi Bioscience as specified below. In addition to reporting a lactation case during the study, investigators should monitor for lactation cases that occur up to 1 week after the last dose of protocol-required therapies.

## **11. WITHDRAWAL FROM TREATMENT, PROCEDURES, AND STUDY**

### **11.1. Discontinuation from Investigational Product**

The following events are considered sufficient reasons for discontinuing a subject from the IP:

- AE(s) (that are intolerable)
- Disease progression
- Physician decision
- Withdrawal of consent (from treatment only)
- Death
- Lost to follow up
- Protocol violation
- Other (to be specified on the CRF)

The reason for treatment discontinuation should be recorded in the CRF and in the source documents.

### **11.2. Discontinuation from the Study**

The following events are considered sufficient reasons for discontinuing a subject from the study:

- Withdrawal of consent
- Death
- Lost to follow up
- Protocol violation
- Other (to be specified on the CRF)

The reason for study discontinuation should be recorded in the CRF and in the source documents.

At the time of withdrawal, it should be determined whether the subject is withdrawing from treatment alone, or from treatment and collection of further data (e.g., survival). Every effort should be made to collect survival data after subject withdraws from treatment.

Subjects have the right to withdraw from the study at any time and for any reason without prejudice to his or her future medical care by the physician or at the institution.

